6.2 DETAILS OF TRIAL PROCEDURES AT SELECTED VISITS

6.2.1 Screening period

After having been informed about the trial, all subjects will provide written informed consent in accordance with GCP and local legislation prior to enrolment in the trial.

For information regarding laboratory tests (including drug and virus screening), ECG, vital signs, and physical examination, refer to Sections [5.2.1](#) to [5.2.5](#).

If possible, spare subjects will be provided for each group to guarantee the start of a complete group. The spare subjects will participate in all trial activities up to Day 1, i.e. on Day -1 they will be admitted to the clinic and all examinations, which have been scheduled up to drug administration on Day 1 will be performed. The spare subjects from one group will be given the option to participate in the next planned group.

6.2.2 Treatment period

On Day -1 trial participants will be admitted to the trial site and kept for 24 h following drug administration. The subjects will be allowed to leave the trial site on Day 2 after formal

Proprietary confidential information © 2021 Boehringer Ingelheim International GmbH or one or more of its affiliated companies

assessment and confirmation of their fitness. On all other trial days, the trial assessments will be performed in an ambulatory fashion.

For details on time points and procedures for collection of plasma samples for PK, [REDACTED] and [REDACTED] analysis, refer to [Flow Chart](#) and in the Laboratory Manual.

The safety measurements performed during the treatment period are specified in Section [5.2](#) of this protocol and in the Flow Chart. AEs and concomitant therapy will be assessed continuously from obtaining subject's written informed consent until the end of trial examination.

For details on times of all other trial procedures, refer to the Flow Chart.

6.2.3 Follow-up period and trial completion

For AE assessment, laboratory tests, recording of ECG and vital signs, and physical examination during the follow-up period, see Section 5.2.

Subjects who discontinue treatment before the end of the planned treatment period should undergo the EoT Visit.

If needed in the opinion of the investigator, additional visits may be scheduled after the EoT Visit for continued safety monitoring.

All abnormal values (including laboratory parameters) that are assessed as clinically relevant by the investigator will be monitored using the appropriate tests until a return to a medically acceptable level is achieved.

Safety follow-up observational period will continue for 10 weeks after BI 695501 administration to collect AEs (SAEs).

The subjects are to be instructed to contact the investigator or his/her designee in case of occurrence of any AEs, any additional concomitant drug or if they undergo any medical treatment or any surgical procedure during the observational period until the safety follow-up (EoS) visit call. Subjects will be contacted by the investigator or designee 10 weeks after administration of the trial medication to collect the information on subject's wellbeing and document all AEs (SAEs) and concomitant medication.

All AEs, serious and non-serious, will be followed up until they have normalized or been sufficiently characterized and documented in the safety database.

7. STATISTICAL METHODS AND DETERMINATION OF SAMPLE SIZE

7.1 NULL AND ALTERNATIVE HYPOTHESES

The relative bioavailability of 40 mg BI 695501 100 mg/mL formulation (T) versus 40 mg BI 695501 50 mg/mL formulation (R) will be estimated by the ratios of the geometric means (T/R) for each primary endpoint, and their corresponding 2-sided 90% confidence intervals (CIs) will be provided. This method corresponds to the two one-sided t-test procedure, each at the 5% significance level. Since the main focus is on estimation and not testing, a formal hypothesis test and associated acceptance range is not specified and no significance level adjustment for multiple testing will be applied.

7.2 PLANNED ANALYSES

7.2.1 Analysis sets

Statistical analyses will be based on the following analysis sets:

- Treated set (TS): The treated set includes all subjects who were randomized and treated with at least one dose of study drug. The TS will be used for safety analyses.
- Pharmacokinetic parameter analysis set (PKS): This set includes all subjects in the treated set (TS) who provide at least one PK endpoint that was defined as primary and was without important protocol deviations or violations thought to significantly affect the PK of BI 695501 (as specified in 7.2.1.2). Descriptive and model based analyses of PK parameters will be based on the PKS.

Descriptions of additional analysis sets may be provided in the TSAP.

Adherence to the protocol will be assessed by the trial team. Important protocol deviation (iPD) categories will be suggested in the iPD specification file. IPDs will be identified no later than in the Report Planning Meeting, and the iPD categories will be updated as needed.

7.2.1.1 Pharmacokinetics

The pharmacokinetic parameters listed in Section 2.1 [REDACTED] for drug BI 695501 will be calculated according to the relevant procedures of the Sponsor.

Pharmacokinetic parameters of a subject will be included in the analysis unless the subject has an important protocol violation relevant for the evaluation. Reasons for exclusion of single pharmacokinetic parameters can for example be:

- Time deviations
- Use of restricted medications
- Dosing errors

Whether a protocol violation is important will be decided no later than in the Report Planning Meeting. It will also be decided in the Report Planning Meeting which subjects are to be excluded from the PKS. Subjects who are not included in the PKS (refer to Section 7.2.1) will be reported with their individual plasma concentrations and individual PK parameters;

Proprietary confidential information © 2021 Boehringer Ingelheim International GmbH or one or more of its affiliated companies

however, they will not be included in descriptive statistics for plasma concentrations, PK parameters or other statistical assessments.

In case a pre-dose concentration value is greater than 5% of Cmax, the subject's PK data will not be included in any statistical evaluations, in accordance with international guidance. The individual PK parameters of such a subject will be calculated and listed separately. If a predose concentration is above the limit of quantification, but less than or equal to 5% of the subject's Cmax value, the subject's data without any adjustments will be included in all PK measurements and calculations.

Details of the analysis and presentation of PK data will be provided in the Trial Statistical Analysis Plan (TSAP).

Only concentration values within the validated concentration range and actual sampling times will be used for the calculation of pharmacokinetic parameters. Concentrations used in the pharmacokinetic calculations will be in the same format provided in the bioanalytical report, (that is, to the same number of decimal places provided in the bioanalytical report).

7.2.2 Primary endpoint analyses

Primary analyses

The primary analysis is based on the PKS (see Section [7.2.1.1](#)). The statistical model used for the analysis of the primary endpoints will be an analysis of covariance (ANCOVA) model on the logarithmic scale. That is, the PK endpoints will be log-transformed (natural logarithm) prior to fitting the ANCOVA model. This model will include effects accounting for the following sources of variation: 'treatment', 'location of trial medication injection' and 'baseline body weight'. The model is described by the following equation:

$$y_{kjm} = \mu + \tau_k + \varphi_j + \beta \cdot \text{weight}_{km} + e_{kjm}, \text{ where}$$

y_{kjm} = logarithm of response on subject m receiving treatment k at location j,
 μ = the overall mean,

τ_k = the k^{th} treatment effect, $k = 1, 2$,

φ_j = the j^{th} effect of location (thigh, abdomen), $j = 1, 2$,

β = the slope parameter for the baseline body weight covariate,

weight_{km} = baseline body weight of subject m receiving treatment k

e_{kjm} = the random error associated with the m^{th} subject who received in location j treatment k

where $e_{kjm} \sim N(0, \sigma_k^2)$ are independent random variables.

Point estimates for the ratios of the geometric means (T/R) for the primary endpoints (see Section [2.1](#)) and their two-sided 90% confidence intervals (CIs) will be provided.

For each endpoint, the difference between the expected means for log(T)-log(R) will be estimated by the difference in the corresponding adjusted means (Least Squares Means).

Proprietary confidential information © 2021 Boehringer Ingelheim International GmbH or one or more of its affiliated companies

Additionally their two-sided 90% confidence intervals will be calculated based on the residual error from the ANCOVA and quantiles from the t-distribution. These quantities will then be back-transformed to the original scale to provide the point estimate and 90% CIs for each endpoint.

In addition to the model based approach all parameters will be calculated and analysed descriptively.

7.2.3 Secondary endpoint analyses

Not applicable as no secondary endpoints specified.

7.2.5 Safety analyses

Safety will be analysed based on the assessments described in Section [2.2.2.2](#). All treated subjects (TS, refer to Section [7.2](#)) will be included in the safety analysis. Safety analyses will be descriptive in nature and based on BI standards. No hypothesis testing is planned.

For all analyses, the treatment actually administered (= treatment at onset) to the subject will be used (any deviations from the randomised treatment will be discussed at the Report Planning Meeting).

Treatments will be compared in a descriptive way. Tabulations of frequencies/proportions will be used to evaluate categorical (qualitative) data, and tabulations of descriptive statistics will be used to analyse continuous (quantitative) data.

Adverse events will be coded using the Medical Dictionary for Regulatory Activities (MedDRA). All events with an onset after the first dose of trial medication up to a period of 10 weeks after the last dose of the trial medication (i.e., end of the REP) will be assigned to the treatment phase for evaluation, and will be referred to as treatment emergent adverse events (TEAEs). Frequency, intensity and causal relationship of AEs will be tabulated by treatment, primary system organ class and preferred term. SAEs and other significant AEs (according to ICH E3), and protocol-specified AESIs (see Section [5.2.6.1](#)), will be listed separately.

Proprietary confidential information © 2021 Boehringer Ingelheim International GmbH or one or more of its affiliated companies

The number and percentage of subjects with injection site reactions (assessed at Day 1 from the time of the injection until Day 2, prior to discharge from the trial site) will be summarized by treatment for each injection site reaction.

Previous and concomitant therapies will be presented per treatment group without consideration of time intervals and treatment periods.

Laboratory values taken after the first dose of trial medication up to a period of 10 weeks after the last dose of the trial medication will be assigned to the treatment phase for evaluation. Descriptive statistics of laboratory values over time and for the change from baseline will be provided for each treatment group. Laboratory parameters will be compared to their reference ranges and frequency tables will be provided for the number of subjects within and outside the reference range.

Observed values and changes from baseline in BP (systolic and diastolic), PR, and body temperature will be summarized by treatment group.

Details of the presentation and analysis of safety data will be provided in the TSAP.

Relevant ECG findings will be reported as AEs.

7.2.6 Interim analyses

No interim analysis is planned.

7.3 HANDLING OF MISSING DATA

7.3.1 Safety

With respect to AE analysis, missing relationship will be imputed to “yes”. For other safety evaluation, no imputation of missing data is planned.

7.3.2 Pharmacokinetics

Handling of missing PK data will be performed according to the relevant procedures of the Sponsor.

Drug concentration data identified with NOS (no sample available), NOR (no valid result), NOA (not analysed) will not be considered for the non-compartmental analysis and the creation of graphs, except for concentration values in the lag phase identified as BLQ which will be set to zero. The lag phase is defined as the period between time zero and the first time point with a concentration above the quantification limit.

Descriptive statistics of parameters are calculated only when a parameter value is available for at least 2/3 of the treated individuals. If the actual sampling time is not recorded or is missing for a certain time point, the planned time will generally be used for this time point instead. PK parameters that cannot be determined will be identified as “not calculated”.

7.4 RANDOMISATION

Subjects will be randomized to one of the two treatments in a 1:1 ratio. The block size will be documented in the CTR. The randomization will be stratified by trial site for logistical reasons.

The sponsor will arrange for the randomization as well as packaging and labelling of trial medication. The randomization list will be generated using a validated system, which involves a pseudo-random number generator and a supplied seed number so that the resulting allocation is both reproducible and non-predictable.

The randomization list will contain additional blocks to allow for subject replacement (refer to Section [3.3.5](#)).

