Main inclusion criteria	Healthy male/female subjects, age of 18 to 55 years (inclusive), body mass index (BMI) of 18.5 to 29.9 kg/m ² (inclusive)
Test product	BI 695501 Solution for injection in prefilled syringe (T)

Proprietary confidential information © 2021 Boehringer Ingelheim International GmbH or one or more of its affiliated companies

dose	40 mg / 0.4 mL / 100 mg/mL
mode of administration	Subcutaneous injection
Reference product	BI 695501 Solution for injection in prefilled syringe (R)
dose	40 mg / 0.8 mL / 50 mg/mL
mode of admin.	Subcutaneous injection
Duration of treatment	Single dose administration trial followed by a 57-day observation period and up to 70 days safety follow up period
Statistical methods	
Relative bioavailability of 40 mg/ 0.4 ml BI 695501 formulation (Test, T) compared to 40 mg/ 0.8 ml of BI 695501 formulation (Reference, R) will be estimated by the ratios of the geometric means (T/R) for the primary endpoints. Additionally, their two-sided 90% confidence intervals (CIs) will be provided. This method corresponds to the two one-sided t-test procedure, each at a 5% significance level. Since the main focus is on estimation and not testing, a formal hypothesis test and associated acceptance range is not specified. The statistical model will be an analysis of covariance (ANCOVA) on the logarithmic scale including effects for 'treatment', 'location of trial medication injection' and 'baseline body weight'. CIs will be calculated based on the residual error from the ANCOVA.
 
Descriptive statistics will be calculated for all endpoints.

Proprietary confidential information © 2021 Boehringer Ingelheim International GmbH or one or more of its affiliated companies

FLOW CHART

Visit	Day	Planned time [h:min]	Approx. time (actual time) [h:min] ⁶	Event and comment	Laboratory/ Urinalysis ⁴	Injection site / Local tolerability Assessment	PK _{blood}	Physical Exam	12-lead ECG	Vital signs (BP, PR and Temp ³)	AE/Concomitant Mediation
1	-28 to -2			Screening	A ⁷			X	X	X	▲ ▼
	-1			Admission to trial center	B ^{7,8}			X	X	X	X
1	-1:00	7:00	Predose		X	X	X				X
	0:00	8:00	Drug administration								
	0:30	8:30			X						X
	4:00	12:00			X	X				X	X
	12:00	20:00				X					X
2	24:00	8:00	Discharge from trial site		X	X		X	X	X	X
3	48:00	8:00	Ambulatory visit			X					X ▲
4	72:00	8:00	Ambulatory visit			X					
5	96:00	8:00	Ambulatory visit			X					
6	120:00	8:00	Ambulatory visit			X					
7	144:00	8:00	Ambulatory visit			X					

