4.1.4 Drug assignment and administration of doses for each subject

This is a single dose trial. All subjects will receive one of two possible treatments in a randomized order. The treatments to be evaluated are summarised in Table 4.1.4: 1 below.

Table 4.1.4: 1 Dosage and treatment schedule

Treatment	Substance	Formulation	Unit strength	Dosage	Total dose
T (Test)	BI 695501	Solution for injection in PFS	100 mg/mL	0.4 mL	40 mg
R (Reference)	BI 695501	Solution for injection in PFS	50 mg/mL	0.8 mL	40 mg

The prefilled syringes should be taken out of the fridge and wait approximately 30 minutes before administration, to permit the medication to warm to room temperature. Injecting cold medication can cause discomfort. Once taken out of the refrigerator, the trial medication should be administered within approx. 1 hour. A syringe must not be used if it is frozen or if it has been left in direct sunlight.

Trial medication will be administered as a single, s.c. injection while the subject is in a supine position by the trained investigator or designee. The time, injection location, and any difficulties with injection of the trial medication administration will be recorded in the eCRF. The location for the trial medication injection will be the lower abdomen (excluding a 2-inch [5-cm] area around the navel) or upper thigh. Each injection site should be used for at least 60 subjects (~30%), preferably 100 subjects (i.e. 50%) of the study population. Detailed “Instructions for use” are provided in the [Appendix 10.1](#) and will be provided in the ISF. Subjects will be kept under close medical surveillance until 24 hours following trial medication administration.

Standardized meals will be served during the residential period.

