7.5 DETERMINATION OF SAMPLE SIZE

It is planned to enter a total of N=200 subjects in the trial including up to 10 subjects, that may be considered as non-PK evaluable (refer to Section [7.2](#)), because this sample size is considered sufficient to assess the primary objective of this exploratory trial. With this sample size, the following precision in estimating the ratio of geometric means (T/R) can be expected with 95% probability. Precision is defined as the ratio of upper 90% confidence interval limit (CL) to the relative BA estimate. Note that the precision is independent of the actual ratio of geometric means.

In previous trials (1297.6 and 1297.13) the observed total geometric coefficient of variation (gCV) for the primary endpoints AUC and Cmax were in the range of 25% - 54%. The observed gCVs tended to be higher in trial 1297.6, in which the study drug was injected in lower abdomen only.

For various assumptions of the gCV, Table [7.5: 1](#) provides an overview of the achievable precision for estimating the ratio of geometric means (T/R). For illustrative purposes, the expected 90% confidence intervals are displayed for different values of the ratio T/R of geometric means.

Proprietary confidential information © 2021 Boehringer Ingelheim International GmbH or one or more of its affiliated companies

Table 7.5: 1

Precision that can be expected with 95% probability and illustrative two-sided 90% confidence intervals around the ratios of geometric means (T/R) for different gCVs in a parallel trial ($N=190$) assessing formulation differences

N	gCV [%]	Precision upper CL* / relative BA estimate	90% CI [%] of respective ratio**		
			100	105	110
190	25	1.066	(93.80; 106.61)	(98.49; 111.94)	(103.18; 117.27)
	40	1.105	(90.47, 110.54)	(94.99, 116.06)	(99.51, 121.59)
	50	1.131	(88.44, 113.07)	(92.86, 118.72)	(97.28, 124.38)

*CL = confidence interval limit

**Ratio of geometric means (T/R) for a PK endpoint is defined by $\exp(\mu_T)/\exp(\mu_R)$.

The expected 90% confidence interval limits in the table were derived by

$$CI \text{ limit}_{\text{upper},\text{lower}} = \exp(\ln(\theta) \pm \omega),$$

with θ being the ratio (T/R) on original scale and ω the distance from the estimate θ to either confidence interval limit on the log-scale, which was obtained from the achievable precision on the original scale.

The calculation was performed as described by Julius [R11-5230, Chapter 8] using R Version 4.02.

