### 4.3. CHANGES TO ANALYSIS FROM PROTOCOL

There are no changes in the analysis plans relative to the study protocol.

---

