### 17.1.4. PRIMARY ANALYSIS FOR PHARMACOKINETIC VARIABLES

Relative bioavailability of 40 mg/ 0.4 ml BI 695501 formulation (Test, T) compared to 40 mg/ 0.8 ml of

Document:	BI_1297-0015_SAP_Final_v1.0	Version Number:	Final 1.0
Author:	[REDACTED]	Version Date:	30Sep2022

Template No: CS\_TP\_BS016 – Revision 7

Reference: CS\_WI\_BS005

Effective Date: 01Nov2021

Copyright © 2009, 2010, 2012, 2016, 2018, 2019, 2021 [REDACTED]. All Rights Reserved. The contents of this document are confidential and proprietary to [REDACTED] Holdings Inc. and its subsidiaries. Unauthorized use, disclosure or reproduction is strictly prohibited.

BI 695501 formulation (Reference, R) will be estimated by the ratios of the geometric means (T/R) for the primary endpoints. Additionally, their two-sided 90% confidence intervals (CIs) will be provided.

The primary PK endpoints for BI 695501 will be estimated using an analysis of covariance (ANCOVA) model on the logarithmic scale (natural logarithm) with effects for treatment, location of trial medication injection and baseline body weight (continuous).

The ANCOVA model is described by the following equation:

$y_{kjm} = \mu + \tau_k + \varphi_j + \beta * \text{weight}_{km} + e_{kjm}$ , where

$y_{kjm}$  = logarithm of PK parameter measured on subject m receiving treatment k at location j,

$\mu$  = the overall mean,

$\tau_k$  = the k-th treatment effect, k = 1, 2 (1=T (BI 0.4 mL), 2=R (BI 0.8 mL)),

$\varphi_j$  = the jth effect of location (thigh, abdomen), j= 1, 2,

$\beta$  = the slope parameter for the baseline body weight covariate,

$\text{weight}_{km}$  = baseline body weight of subject m receiving treatment k, and,

$e_{kjm}$  = the random error associated with the m-th subject who received in location j treatment k,

where  $e_{kjm} \sim N(0, \sigma_k^2)$  are independent random variables.

The following SAS code will be used:

(M1) 

```
PROC MIXED data= ADPP<restricted to parameter> METHOD=REML;
  CLASS TRTP (ref="R") Location;
  MODEL AVAL = TRTP Location BASE_WEIGHT /DDFM=KR;
  LSMEANS TRTP;
  ESTIMATE 'BI 695501 T versus R' TRTP 1 -1 /alpha=0.1;
RUN;
```

For model (M1), AVAL refers to the PK endpoint value on the logarithmic scale.

For each PK endpoint, (M1) estimates the difference between the means for log(T)-log(R) by the difference in the corresponding adjusted means (least-squares means), and a two-sided 90% CI based on the t-distribution will be computed.

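### Randomisation is stratified by trial site, but the primary ANCOVA has no site term, so the 90% CI may be slightly too wide

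*Protocol*

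**What the plan says.** - **Randomisation.** The trial runs at two sites (Protocol synopsis and 8.7) with 1:1 allocation. Protocol 7.4 adds: "The randomization will be stratified by trial site for logistical reasons". No other stratification factor is named.
- **Primary model, protocol.** Section 7.2.2: "This model will include effects accounting for the following sources of variation: 'treatment', 'location of trial medication injection' and 'baseline body weight". The synopsis lists the same three effects. The CI is built from the ANCOVA residual error and t quantiles.
- **Primary model, SAP.** Section 17.1.4 repeats the equation, and its SAS code reads "MODEL AVAL = TRTP Location BASE_WEIGHT /DDFM=KR". There is no site term and no RANDOM or REPEATED statement. SAP 4.3 states: "There are no changes in the analysis plans relative to the study protocol".
- **Injection location.** Protocol 4.1.4 sets a quota for the trial as a whole, not per site: "Each injection site should be used for at least 60 subjects (~30%), preferably 100 subjects (i.e. 50%) of the study population".
- **Role of the CI.** Protocol 7.1 makes estimation the aim; "a formal hypothesis test and associated acceptance range is not specified".

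The text available for review gives no reason for leaving site out and no sensitivity analysis that includes it.

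**The concern.** Stratifying by site with 1:1 allocation keeps the arms balanced within each site, so a difference in exposure level between sites largely cancels out of T minus R on the log scale. The true variance of the contrast then reflects within-site variation only. A model without site does not recognise this. Whatever part of the site difference is not carried by weight or injection location goes into the residual, and the reported standard error exceeds the true one.

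The ratio with its 90% CI is the only inferential result of the trial. What is at stake is whether that interval has its stated coverage, and whether precision the design has already secured is given away in the analysis. The validity of the estimate is not in question.

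**Working it through.** **Inputs from the documents.** 190 analysed subjects, two-sided 90% CI, and total gCV of 25%, 40% and 50% as tabulated, with 54% as the top of the observed range (all Protocol 7.5 and Table 7.5:1).

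**Assumptions.** The documents give no site effect. The ratio of geometric mean exposure between sites, beyond weight and location, is taken as 1.1 or 1.2, with 1.05 as a smaller case. The share of subjects at one site, p, is 0.5 unless stated. The gCV is read as the total variation left after weight and location, site included.

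**Step 1: reproduce Table 7.5:1.** With V = ln(1 + gCV²),

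precision = exp{ t(0.95; 188) × √[ (4V/190) × χ²(0.95; 188)/188 ] },

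where t = 1.6530 and χ² = 220.99.

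| gCV | V | Computed | Table |
|---|---|---|---|
| 25% | 0.06062 | 1.0661 | 1.066 |
| 40% | 0.14842 | 1.1054 | 1.105 |
| 50% | 0.22314 | 1.1307 | 1.131 |

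The table is reproduced without any credit for a site term.

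**Step 2: variance due to site.** B = p(1 − p)(ln ratio)². With p = 0.5:
- ratio 1.1: 0.25 × 0.09531² = 0.00227
- ratio 1.2: 0.25 × 0.18232² = 0.00831

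**Step 3: excess CI width when site is omitted.** Excess = √[V/(V − B)] − 1 on the log scale. At gCV 25% and ratio 1.2 this is √(0.06062/0.05231) − 1 = 7.7%. Coverage is P(|t186| < t(0.95; 186) × √[V/(V − B)]).

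| gCV | Ratio 1.05 | Ratio 1.1 | Ratio 1.2 |
|---|---|---|---|
| 25% | 0.5% | 1.9% (coverage 90.6%) | 7.7% (coverage 92.3%) |
| 40% | 0.2% | 0.8% | 2.9% |
| 50% | 0.1% | 0.5% | 1.9% |
| 54% | 0.1% | 0.4% | 1.7% |

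If the gCV is read as within-site instead, the factor is √(1 + B/V), and the largest entry falls from 7.7% to 6.6%.

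**Step 4: unequal sites, gCV 25%, ratios 1.1 / 1.2.** A 70:30 split gives 1.6% / 6.3%; a 90:10 split gives 0.7% / 2.6%.

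**Step 5: location tracking site.** Because the location quota is trial-wide, location may partly stand in for site. This was simulated with 8000 trials per setting, N = 190, equal sites, assumed blocks of 4 within site, and the model fitted with and without site. Excess width at ratios 1.1 / 1.2:

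| Location pattern | gCV 25% | gCV 50% |
|---|---|---|
| Balanced across sites | 1.9% / 7.7% | 0.5% / 1.9% |
| 80% thigh at one site, 20% at the other | 1.1% / 4.9% | 0.2% / 1.2% |
| Fully aliased with site | 0% / 0% | 0% / 0% |

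The mean error in log T/R was 0.0015 or less throughout, so no bias appeared. In a separate simulation (6000 runs per setting, 190 of 200 subjects kept at random), CI widths with and without site were the same when the sites did not differ.

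**Step 6: absolute size.** Replace V by V − B and use 187 df in Step 1, ratios 1.1 / 1.2:
- gCV 25%: precision moves from 1.0661 to 1.0648 / 1.0613
- gCV 50%: precision moves from 1.1307 to 1.1300 / 1.1281

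The largest shift is 106.61% − 106.13% ≈ 0.5 percentage points on the upper limit at a ratio of 100%.

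**The case against.** The strongest reply is that this is a preference, not an error. The protocol stratifies for logistics and never calls site prognostic. The model adjusts for the two factors the sponsor treats as sources of PK variation, and the synopsis, Protocol 7.2.2 and SAP 17.1.4 agree with one another. The sites share eligibility criteria, a supervised single dose from prefilled syringes and blinded bioanalysis, so a 20% difference beyond weight and location is not suggested by anything in the documents. The 7.7% figure needs the lowest gCV, the larger assumed ratio, equal sites and location unrelated to site. Table 7.5:1 uses total gCV, so the planned precision does not depend on a site term.

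Most of this stands, and it is why the point is minor. It does not remove the point. The motive for stratifying does not alter what blocking does to the variance of the contrast, and the model adjusts for two factors that were not stratified while omitting the one that was.

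The statement that there is no bias also needs a condition: T:R balance within site must roughly survive exclusions and replacements, and the T/R ratio must be the same at both sites. Protocol 3.3.5 gives a replacement the same treatment but does not say the same site. The balance condition argues for a site term, since adjustment would also guard against such imbalance.

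**Conclusion.** The concern holds as a minor point. The only stratification factor is missing from the primary model, and if the sites differ beyond weight and injection location, the 90% CI is conservative. For assumed site ratios of 1.1 to 1.2 and equal sites, the excess log-scale width is 1.9% to 7.7% at gCV 25% and 0.4% to 2.9% across gCV 40% to 54%. It is smaller with unequal sites or when location tracks site, and nil if location and site coincide or if the site difference acts only through weight or location. The true site effect is unknown, so these figures show a range and are not a prediction. With no acceptance range and the planned precision met either way, no conclusion of the trial would change.

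**What to change.** Add trial site as a fixed effect to the primary model in the protocol synopsis, Protocol 7.2.2 and SAP 17.1.4. In the SAP, add a site term to the equation, add the site variable (for example `SITEID`) to the CLASS statement, and use `MODEL AVAL = TRTP Location SITEID BASE_WEIGHT /DDFM=KR;`. If only the SAP is changed, record the departure in SAP 4.3. Add a table of site by injection location; if the two are fully aliased, T/R remains estimable and one of the terms is redundant.

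The cost is one model term, one SAP sentence and one cross-table, with no new data. At N = 190 the residual df fall from 186 to 185, which raises the t quantile by about 0.003%. If the sponsor prefers to keep the present model, the lighter alternative is to justify the omission and prespecify a sensitivity analysis with site. Either should be settled before unblinding.
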